	
specimens on an area of normal tissue within the surgical field using the intraoperative NIR camera. The SOC specimens are to be resected upon the initiation of surgery and imaged on a section of normal tissue (i.e., mesentery). Specimen names and fluorescence status will be dictated by the surgeon and documented in the Imaging Workbook by the research coordinator.
 
At the conclusion of SOC resection, the intraoperative NIR camera will be used to investigate the peritoneal cavity further for evidence of residual metastases highlighted by fluorescence. Additional fluorescent specimens will be imaged in situ and then ex situ on an area of normal tissue within the surgical field prior to sending all surgical specimens to pathology for examination. The fluorescence status of each specimen will then be directly correlated to the histopathological outcomes of each specimen. This study design enables the calculation of pegasitacianine sensitivity, specificity, NPV, and PPV. Additionally, Completeness of Cytoreduction (CC) scores can be calculated following SOC resection and adjusted following the resection of additional fluorescent metastases, if warranted.

Endpoints	
Primary Endpoints:
 
 • Detection of disease left behind following SOC resection of peritoneal metastases. Detection of a single additional tumor-containing specimen excised as a result of pegasitacianine fluorescence will be deemed a clinically significant event (CSE) • Alteration to initial Completeness of Cytoreduction scores following imaging with pegasitacianine 
Secondary Endpoints:
 
 • Acceptable safety profiles following pegasitacianine administration • Sensitivity • Specificity • NPV • PPV
Study Drug	
m /k of pegasitacianine
 
prior to surgery

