At the conclusion of SOC resection, the intraoperative NIR camera will be used to investigate the peritoneal cavity further for evidence of residual metastases highlighted by fluorescence using the approach that is performed for the calculation of the Peritoneal Carcinomatosis Index (i.e., 13 regions). Additional fluorescent specimens will also be imaged prior to excision and subsequently following resection on an area of normal tissue prior to sending all surgical specimens to pathology for examination. The fluorescence status of each specimen, as called out by the surgeon, will then be directly correlated to the histopathological outcomes of each specimen dictated in the final pathology report. This study design enables the calculation of pegsitacianine sensitivity, specificity, NPV, and PPV and the level of the specimens. Additionally, Completeness of Cytoreduction (CC) scores can be calculated following SOC resection and then adjusted following the additional resection of fluorescent metastases otherwise unknown to the surgeon. The schedule of events for this study is presented in Appendix 1.

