6.3 Surgery and Follow-up Visits (Group 1 and 2)

Procedures at the time of cytoreductive surgery

The following procedures will be performed on the day of surgery:

- Record the patient's vital signs (only if they were abnormal at dosing)

- Obtain blood for routine laboratory tests
- Record all medications being taken, including prescription, over-the-counter, and herbal medications
- Discuss with the patient any new or unexpected changes they are feeling
- Record any AEs

Once the patient is under anesthesia, some procedures will occur that would not normally be part of surgery if the patient were not in this study. The SOC surgical procedures will be allowed to continue with the addition of the steps listed below.

- During SOC resection, the surgeon will select up to 15 (10 suspected tumor and 5 normal) specimens that will be imaged using the intraoperative camera on a section of normal tissue following excision (*Note: NIR camera should not be used to examine the peritoneal cavity at this time*)
 - A total of up to 15 specimens are to be imaged: 5 representative normal pieces of tissue and 10 individual suspected tumor specimens
 - The SOC specimens are to be resected upon the initiation of surgery and imaged on a section of normal tissue (i.e., mesentery) immediately following the collection of all SOC samples
 - The width of the camera's field of view is to be confined to a distance of 10 cm. A surgical ruler is to be placed in frame to control the width of the field of view
 - Note: while there are no specimen size stipulations provided in this protocol, the samples must be able to be imaged within the 10 cm wide imaging window.
 - For samples with multiple nodules, individual nodules should be dissected away from the bulk sample and imaged individually as single specimens.
 - Representative normal sections of tissue should be imaged in an analogous manner
- Samples will be imaged using the NIR camera and fluorescence status and specimen name will be dictated by the surgeon for documentation by the clinical research coordinator in the provided Imaging Workbook
- Once the SOC resection is complete, the surgeon will dictate their completeness of cytoreduction score to the clinical research coordinator for documentation prior to examining the peritoneal cavity with the intraoperative NIR camera in search of additional fluorescent metastatic disease that was missed during SOC

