9.3 Rate of Clinically Significant Events

Determining the rate of clinically significant events (CSE) detected by pegasitacianine at the subject-level is the primary objective of this study. CSEs will include pegasitacianine detection of

occult disease not otherwise known by the surgeon to exist, the detection of a positive surgical margin, and accurate identification of tumor negative SOC biopsies. A list of CSEs and their definitions is provided below.

- Detection of Occult Disease or Positive Surgical Margins – identification of tumor-containing tissue due to pgsitacianine fluorescence, confirmed via histopathological analysis, that otherwise went undetected during pre-operative imaging (PET, MRI) or by the surgeon during SOC surgery
 - This occurs when a sample that (1) exhibits fluorescence *in situ* and (2) is pathologically-confirmed as a tumor, is obtained by fluorescence during SOC surgery.
- Tumor Negative SOC Biopsies – during SOC surgery, the surgeon will collect tissue specimens that are suspicious for disease. If those samples do not demonstrate pgsitacianine fluorescence and are found to be devoid of tumor pathologically, those specimens would be included as a tumor negative SOC biopsy
 - This occurs when a sample that (1) exhibits no fluorescence *ex situ* and (2) is pathologically-confirmed as normal tissue, is classified as suspicious tissue during SOC surgery.
- Alteration to the Completeness of Cytoreduction (CC) Score – following the completion of the SOC surgery, the surgeon will document a CC score prior to fluorescence imaging using pgsitacianine. If the surgeon finds residual disease using fluorescence imaging that results in the increase of the CC score, this will be considered a CSE

The number and proportion (with corresponding two-sided exact 95% confidence intervals) of subjects with any CSE will be reported.

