3. STUDY DESCRIPTION

3.1 Study Design

This Phase 2 study will be an interventional, open-label, single arm trial where each patient is his/her own “intrapatient” control using two Groups. All patients will receive a single █ mg/kg dose of pegsitacianine administered █ prior to standard of care surgery.

Patients enrolled in Group 1 of the study will have a biopsy confirmed diagnosis of non-mucinous peritoneal carcinomatosis, defined as less than 50% mucin in the sample, with a suspected Peritoneal Carcinomatosis Index (PCI) greater than or equal to 10. Group 2 of the study will include patients with a suspected PCI greater than or equal to 10 and a biopsy confirmed diagnosis of mucinous peritoneal carcinomatosis, defined as > 50% mucin in the sample. A total of approximately 60 patients will be enrolled across both Groups. Enrollment will be open first to Group 1 with the opportunity to open Group 2 for enrollment at the discretion of the sponsor.

In both Groups 1 and 2, the surgeon will perform their SOC resection of visible metastases and image each resected specimen, and normal specimens on an area of normal tissue outside of the surgical field using the intraoperative NIR camera; no NIR imaging of the peritoneal cavity will be performed at this time. At the conclusion of SOC resection, the intraoperative NIR camera will be used to investigate the peritoneal cavity further for evidence of residual metastases highlighted by fluorescence using an approach similar to that performed for the calculation of the Peritoneal Carcinomatosis Index (i.e., 13 regions). Additional fluorescent specimens will also be imaged on an area of normal tissue within the surgical field prior to sending all surgical specimens to pathology for examination. The fluorescence status of each specimen will then be directly correlated to the histopathological outcomes of each specimen. This study design enables the calculation of pgsitacianine sensitivity, specificity, NPV, and PPV. Additionally, Completeness of Cytoreduction (CC) scores can be calculated following SOC resection and then adjusted following the additional resection of fluorescent metastases. The schedule of events for this study is presented in [Appendix 1](#).

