5. ANALYSIS ENDPOINTS

5.1 Efficacy Endpoints

5.1.1 Clinically Significant Event Endpoints

The primary endpoint will include the identification of a clinically significant event (CSE) detected by pegasitacanine. CSEs will include increase in the Completeness of Cytoreduction

score following standard of care surgery, pegasitacianine detection of occult disease not otherwise known by the surgeon to exist, the detection of a positive surgical margin, and accurate identification of tumor negative SOC biopsies. A list of CSEs and their definitions is provided below.

- Detection of Occult Disease or Positive Surgical Margins – identification of tumor-containing tissue due to pegasitacianine fluorescence, confirmed via histopathological analysis, that otherwise went undetected during pre-operative imaging (PET, MRI) or by the surgeon during SOC surgery.
 - This occurs when a sample that (1) exhibits fluorescence *in situ* and (2) is pathologically-confirmed as a tumor, is obtained by fluorescence during SOC surgery.
- Tumor Negative SOC Biopsies – during SOC surgery, the surgeon will collect tissue specimens that are suspicious for disease. If those samples do not demonstrate pegasitacianine fluorescence (e.g. do not exhibit fluorescence *ex situ*) and are found to be devoid of tumor pathologically, those specimens would be included as a tumor negative SOC biopsy.
 - This occurs when a sample that (1) exhibits no fluorescence *ex situ* and (2) is pathologically-confirmed as normal tissue, is classified as suspicious tissue during SOC surgery.
- Alteration to the Completeness of Cytoreduction (CC) Score – following the completion of the SOC surgery, the surgeon will document a CC score prior to fluorescence imaging using pegasitacianine. If the surgeon finds residual disease that results in the increase of the CC score, this will be considered a CSE.

A subject with any CSE will be considered a CSE responder.

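### The CC-score event differs in direction and timing between sections, no listed step records the score it needs, and it lacks the pathology check required for occult disease

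*Protocol*

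**What the plan says.** **Event definition.** Protocol 9.3 has the surgeon document a CC score after standard-of-care (SOC) surgery and before fluorescence imaging, then states: "If the surgeon finds residual disease using fluorescence imaging that results in the increase of the CC score, this will be considered a CSE". SAP 5.1.1 has the same rule without naming the imaging: "If the surgeon finds residual disease that results in the increase of the CC score, this will be considered a CSE". SAP 5.1.1 makes a subject with any CSE a responder, and SAP 7.10.1.1 reports responders and each CSE type with Clopper-Pearson 95% intervals.

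**Endpoint list.** The Protocol Summary gives a separate primary endpoint with no direction: "Alteration to initial Completeness of Cytoreduction scores following imaging".

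**Design text.** The Summary says the score can be "adjusted following the resection of additional fluorescent metastases, if warranted". Protocol 3.1 says "then adjusted following the additional resection of fluorescent metastases otherwise unknown to the surgeon", and SAP 3.1 says "then adjusted following the additional resection of fluorescent metastases". None of the three gives a direction.

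**Collection.** In Protocol 6.3, "the surgeon will dictate their completeness of cytoreduction score to the clinical research coordinator for documentation prior to examining the peritoneal cavity". After the sweep, the surgeon dictates only fluorescence status and specimen name. Neither schedule of events lists a CC score. SAP 7.9.5 names one undifferentiated cytoreduction score, although the same list names two PCI scores (suspected and fluorescence imaging).

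**The concern.** An event defined as a change between two scores needs a direction, a reference score, a time for the second score and a step that records it. Here only the reference score is fixed.

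The time of the second score decides what is measured. A score revised when missed disease is found describes how incomplete the SOC resection was. A score taken once that disease is out describes the final result. The study pools up to 10 centers, and SAP 7.6 makes no allowance for center. If sites read the rule differently, the CC component mixes two measurements.

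Confirmation is a second gap. The occult-disease CSE requires histology; the CC rule does not mention it. Under the pathology footnote to the schedules, results may come up to 10 days after surgery, so a score revised in theatre would often precede them. A fluorescent area that proves benign could then make the patient a responder.

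Protocol 9.1 gives the purpose of enrolling about 60 patients as better endpoint estimates for powering later studies. A component without a fixed meaning serves that purpose poorly.

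**Working it through.** The plan gives no figure for this component and no power calculation, so there is nothing to reproduce. The check compares the passages and then shows scale.

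**Step 1: direction.** The wording of 9.3 (residual disease found, score rises) implies that a higher score means less complete cytoreduction. The Appendix 2 scale is not in the text available to me, so this direction is inferred from 9.3.

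**Step 2: timing.** Let S0 be the score before the NIR sweep, S1 the score with the newly found lesions taken as still present, and S2 the score after those lesions are fully removed.

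- Finding disease can leave completeness unchanged or worse, so S1 ≥ S0. An increase is possible.
- Removing all of it leaves completeness no worse than first judged, so S2 ≤ S0. An increase is not possible.

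If the score is adjusted after resection and only an increase counts, the CC component is about zero. The exception is found disease that is not fully removed.

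**Step 3: three kinds of patient.**

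| Patient | Increase, scored on finding | Increase, scored after full removal | Any alteration |
|---|---|---|---|
| Confirmed residual tumour, large enough to change category | CC event | No CC event | Depends on timing |
| Fluorescent area, score revised, pathology negative | CC event | No CC event | Depends on timing |
| Score falls after further resection | No CC event | No CC event | CC event |

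The first patient is a responder in every column, through the occult-disease CSE. The second becomes a responder on the strength of the CC rule alone, unless another CSE applies. The third is hypothetical, since no passage describes a fall; it shows how the Summary and 9.3 can differ.

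**Step 4: scale.** Assume all 60 patients are evaluable. The Clopper-Pearson limits for x events in n are the 0.025 quantile of Beta(x, n−x+1) and the 0.975 quantile of Beta(x+1, n−x). For x = 0 the upper limit is 1 − 0.025^(1/60) = 6.0%.

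| Reading | Assumed rate | Events | 95% interval |
|---|---|---|---|
| After full removal | 0 by construction | 0/60 | 0 to 6.0% |
| On finding | 5% | 3/60 | 1.0 to 13.9% |
| On finding | 10% | 6/60 | 3.8 to 20.5% |
| On finding | 20% | 12/60 | 10.8 to 32.3% |
| On finding | 30% | 18/60 | 18.8 to 43.2% |

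The 5% to 30% range is assumed; the documents give no rate.

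**Step 5: effect on the any-CSE rate.** Confirmed residual tumour found by fluorescence contributes the same under either timing. Each patient whose only CSE is an unconfirmed CC revision adds 1/60 = 1.7 percentage points. The documents do not allow that number of patients to be estimated. Protocol 1.2 reports earlier specificity of 75% in breast cancer and 57% in head and neck cancer, so false-positive fluorescence is foreseeable, but those are different tumours.

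**The case against.** The best defence is that the operative definitions agree. Protocol 9.3 and SAP 5.1.1 both start from the pre-NIR score and count an increase when residual disease is found, and SAP section 1 lets the SAP prevail on analysis. The adjustment passages are design description. Adjusting a score after resection can mean correcting the SOC score upward once missed disease has been shown, which fits 9.3.

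That stands to this extent: a reader might infer that the sections define opposite events, and the documents do not support it. No passage states a decrease. What remains is that direction differs between the Summary and 9.3, and the time of the second score is not fixed.

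A reader might also infer that no second score is collected. That goes too far. The design text foresees an adjusted score, and the Imaging Workbook, eCRF and table specifications are not among the documents. What can be said is that 6.3 lists no step to record one.

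A third tempting inference is that patients with confirmed residual tumour go uncounted. They do not; the occult-disease CSE captures them.

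On pathology, the Statistical Analysis row of the Summary speaks of deposits confirmed as tumour, and the CC score is by nature a surgeon's judgement. But that row does not govern the CC rule, which is silent. The SAP's omission of the imaging phrase matters little, since SAP 5.1.1 opens by tying CSEs to detection by the agent.

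**Conclusion.** The point holds as an inconsistency in a primary endpoint. Direction (increase or any alteration) and timing (on finding or after resection) differ between sections, no listed step records the second score, and the CC rule has no pathology requirement.

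Read as an increase scored after full removal, the CC component would be about zero: 0/60, interval 0 to 6.0%. This rests on the scale direction implied by 9.3, on complete removal of the found disease, and on 60 evaluable patients. Under the other reading the rate is unknown.

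The exposure is mainly the separately reported CC component and responders created by unconfirmed findings. The any-CSE rate is otherwise largely protected. In a pilot not powered for hypothesis testing, this should be corrected, but it does not invalidate the study.

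**What to change.** - **Protocol 6.3 and eCRF:** record a second CC score after the NIR sweep and before excision, reflecting the fluorescent lesions as if left in place.
- **Protocol 9.3 and SAP 5.1.1:** define the event as a shift from the pre-NIR score to a less complete category, attributable to fluorescence, and counted at analysis only if at least one responsible lesion is confirmed as tumour. Restore the reference to fluorescence imaging in the SAP.
- **Post-resection score:** if one is kept, report it separately as a description of the final result.
- **Alignment:** use the same direction and time point in the Protocol Summary, Protocol 3.1 and SAP 3.1, and name each score in SAP 7.9.5.
- **Patients already operated on:** state which scores were recorded and when, and list patients whose second score has no known time point.

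The cost is one dictated value per patient, one eCRF field and wording changes. Resection itself is unaffected. The pathology condition may lower the CC event rate slightly.

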9.4 Imaging Analysis

Diagnostic performance of pgsitacianine will be assessed at the level of the specimen by calculating the *ex situ* sensitivity, specificity, PPV, and NPV of pgsitacianine in detecting tumor containing tissue. The *ex situ* fluorescence status of collected SOC and pgsitacianine guided specimens will be compared to the histological analyses of the collected specimens (which is used to determine each sample's status as true/false positive/negative). For determining these operating characteristics, consider the following definitions:

- False positive is defined as “fluorescence was observed on the specimen but the specimen was not found to have tumor via histological analysis”.
- False negative is defined as “no fluorescence was observed on the specimen but the specimen was found to have tumor via histological analysis”.

- True positive is defined as “fluorescence was observed on the specimen and the specimen was found to have tumor via histological analysis”.
- True negative is defined as “no fluorescence was observed on the specimen and the specimen was found not to have tumor via histological analysis”.

The number of specimens in each category (each combination of true/false positive/negative), along with the true/false positive/negative rates (and corresponding exact two-sided 95% confidence intervals) will be reported. These rates will be used to determine pegsitacianine’s tumor detection sensitivity, specificity, PPV, and NPV using the following equations:

$$\text{Sensitivity} = \frac{\text{\# of True Positive Specimens}}{\text{\# of True Positive + False Negative Specimens}}$$

$$\text{Specificity} = \frac{\text{\# of True Negative Specimens}}{\text{\# of True Negative Specimens + \# of False Positive Specimens}}$$

$$\text{PPV} = \frac{\text{\# of True Positive Specimens}}{\text{\# of True Positive + False Positive Specimens}}$$

$$\text{NPV} = \frac{\text{\# of True Negative Specimens}}{\text{\# of Tumor Negative + False Negative Specimens}}$$

These rates will be reported along with exact two-sided 95% confidence intervals.

9.5 Quantification of Fluorescence Intensity

Specimen-to-background (SBR) ratios and tumor-to-background (TBR) ratios will also be calculated using white light and NIR images of both SOC and pegsitacianine guided specimens. SBRs will be calculated using *ex situ* images of collected specimens. The equation for calculating SBR is listed below.

$$\text{SBR} = \frac{\text{Mean Fluorescence Intensity (Specimen)}}{\text{Mean Fluorescence Intensity (Normal Tissue)}}$$

TBR is calculated in the same way, but refers specifically to samples that are histologically confirmed as tumor.

The mean fluorescence intensity of the specimen, of the background, and the SBR (or TBR) of each specimen will be summarized by the histologically-confirmed tumor status (either “tumor present” or “tumor not present/normal tissue”).

9.6 Diagnostic Imaging Sensitivity Analyses

In this pilot study we are assuming that any fluorescence is indicative of tumor presence. To assess how the amount of observed fluorescence (e.g., the SBR or TBR) may affect the diagnostic accuracy of pegsitacianine, a receiver operating characteristic (ROC) analysis will be performed on all specimens using the observed thresholds of SBR and TBR. The corresponding ROC curve will be provided along with the area under the curve (AUC).

There is potential for within-subject correlation to bias our estimates of pegsitacianine's diagnostic accuracy. To assess this issue, an ROC curve will be constructed from a mixed model that clusters specimens by the subject they originated from. We will compare the AUC of the mixed effects ROC curve to the standard ROC curve to assess if within-subject correlation is causing significant bias in our analyses. If it is determined that significant bias has been introduced, additional analyses on secondary endpoints may be performed to assess the diagnostic accuracy of pegsitacianine.

